### 9.3 STATISTICAL METHODS

Detailed methodology for summary and statistical analyses of the data collected in this study will be documented in a statistical analysis plan (SAP), which will be maintained by the Sponsor. The SAP may modify the plans outlined in the protocol; however, any major modifications will also be reflected in a protocol amendment. The SAP will be finalized before database lock and will describe the analysis populations to be included in the analyses, and procedures for accounting for missing, unused, and spurious data. The SAP will supersede this section of protocol in the event of divergence. This section is a summary of the planned statistical analyses of the primary and secondary endpoints.

#### 9.3.1 General

Statistical analyses will be performed using SAS® v9.4 or higher (SAS Institute, Cary NC, USA) and all analysis will be described in the SAP finalized before database lock.

The standard summary statistics for continuous variables are sample size (n), mean, standard deviation (SD), median, minimum, and maximum. The standard summary statistics for categorical variables are frequencies and percentages. Time to event variables will be summarized using the Kaplan-Meier method. Where confidence limits are appropriate, the confidence level will be 95% (two-sided), unless otherwise stated.

Individual data (including relevant derived variables) will be presented by parameter in listings. Results of statistical analyses, descriptive summary statistics and supportive listings will also be presented.

### 9.3.2 Efficacy Analysis

#### Solid Tumour Cohort

The secondary endpoint of ORR will be defined as the proportion of subjects with BOCR of either a CR or PR as assessed by the Investigator using RECIST v1.1 in the Response Evaluable Population as both unconfirmed or confirmed status. ORR will be reported as a proportion along with the corresponding 2-sided 95% Clopper-Pearson exact CI.

A sensitivity analysis of the primary endpoint will be performed in the Response Evaluable Population.

Other secondary and exploratory endpoints are defined as follows for the whole cohort or analysed by tumour type:

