#### 4.1.2.3 Disease Evaluation

For subjects in the solid tumours cohort, the on-treatment radiographic assessments of chest, abdomen, and pelvis will be performed per standard of care intervals throughout the course of the study.

The first radiographic scan after receiving SUPLEXA will be performed at Week 6-12 weeks after the 1st SUPLEXA infusion and thereafter every 6-12 weeks depending on tumour type and as clinically indicated per investigator's discretion.

These scans should be available for assessment by the Sponsor, if requested. The response evaluation will be assessed by the Investigator according to RECIST v1.1 and iRECIST until unequivocal radiographic disease progression, or until the subject starts a subsequent anticancer therapy (whichever comes first). The tumour assessment (imaging) for confirmation of response should be performed no less than 4 weeks after the criteria for response are first met. All radiographic scans will be collected and held for possible future retrospective evaluation by BICR.

For subjects in the haematological malignancies cohort, disease evaluation will be conducted every 4 weeks, as clinically indicated throughout the study.

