#### Type of Subject and Disease Characteristics

##### Solid Tumours

2. Histologically or cytologically confirmed diagnosis of locally advanced or metastatic solid tumour.
3. Have 1 or more tumours measurable based on RECIST v1.1 as assessed by the local site Investigator. Radiographic scans should be obtained within 5 weeks of Screening. Lesions situated in a previously irradiated area are considered measurable if objective progression has been demonstrated following radiation to such lesions.
4. Subjects who did not attain a durable response after receiving at least one standard/approved therapies which may include chemotherapy, targeted agents, radio-, immuno- conjugates, check point inhibitors or where there is no approved therapy. This includes subjects who attained a long-term stable disease (SD), or partial response (PR) are eligible. Long term SD subjects on a checkpoint inhibitor may continue checkpoint inhibitor (CPI) therapy.  
\* Any therapies defined as immunosuppressive require a washout period of at least 4 weeks, defined as 4 weeks (28 days) prior to blood collection for SUPLEXA manufacturing and any SUPLEXA dose administration.

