### 9.2 POPULATION FOR ANALYSES

For purposes of analysis, the following populations are defined:

Population	Description
DLT evaluable Population	All subjects who receive at least 1 dose of study intervention and experience a DLT.
Safety Analysis Set	All subjects who receive at least 1 dose of study intervention.
Response Evaluable Population	All subjects who receive at least 1 dose of study intervention and have measurable disease at baseline and at least one post-baseline tumour assessment per RECIST v1.1.

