##### Exploratory

- DOR will be defined as the time from the first date of objective response (CR or PR) to the first documented date of disease progression or the date of death due to any cause, whichever occurs first. Only subjects with a CR or PR will be included.
- TTR will be defined as the time from the first dose of study intervention to the first date of objective response (CR or PR). Only subjects with a CR or PR will be included.
- CBR will be defined as the proportion of subjects with a CR or PR or SD at 6 months.
- PFS will be defined as the time from the first dose of study intervention to the first documented date of disease progression or the date of death due to any cause, whichever occurs first.
- OS will be defined as the time from the first dose of study intervention to the date of death due to any cause.
- Biomarker change from baseline with time as % and absolute.

Main analyses of the above response-related endpoints will be performed in the Efficacy Evaluable Population using Investigator-assessed response. Sensitivity analyses of the above response-related endpoints may be performed in the Response Evaluable Population using Investigator-assessed response. If response is also assessed by BICR, further sensitivity analyses of the above response-related endpoints may be performed using BICR-assessed response.

CBR will be analysed in a similar manner as the primary endpoint of ORR.

Time-to-event endpoints (DOR, TTR, PFS, TTP, and OS) will be summarized using Kaplan-Meier estimates. If estimable, median, 25th, and 75th percentiles and associated 95% CIs will be presented. A Kaplan-Meier curve will also be generated for each time-to-event endpoint. For time-to event endpoints, censoring rules will be applied as follows. DOR will be censored at the last tumour assessment date. PFS and TTP will be censored at the last tumour assessment date

for subjects with post-baseline assessment (s). OS will be censored at the last known date alive for subjects.

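### Solid-tumour ORR and its sensitivity analysis use the same scan-dependent population, and the Efficacy Evaluable Population is never defined

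*Combined protocol and SAP*

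**What the plan says.** Section 9.3.2 (Solid Tumour Cohort) has the Investigator assess ORR "using RECIST v1.1 in the Response Evaluable Population as both unconfirmed or confirmed status", with an exact Clopper-Pearson 95% interval. The next paragraph reads: "A sensitivity analysis of the primary endpoint will be performed in the Response Evaluable Population".

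Section 9.2 defines three sets: DLT evaluable, Safety and Response Evaluable. To be in the last, subjects must have received at least one dose and "have measurable disease at baseline and at least one post-baseline tumour assessment per RECIST v1.1".

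Further down, under the exploratory endpoints, Section 9.3.2 uses a different scheme: "Main analyses of the above response-related endpoints will be performed in the Efficacy Evaluable Population using Investigator-assessed response". It continues: "Sensitivity analyses of the above response-related endpoints may be performed in the Response Evaluable Population using Investigator-assessed response". It then adds: "CBR will be analysed in a similar manner as the primary endpoint of ORR".

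The Efficacy Evaluable Population is not among the sets in Section 9.2, and it is not in the glossary (Appendix 10). Section 9.3 leaves the description of analysis populations to a SAP to be finalised before database lock. The supplied documents contain no SAP text that defines them.

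**The concern.** A sensitivity analysis should change something that might matter, such as the population, the assessor or the handling of missing data. The one written for ORR changes nothing.

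What most needs testing is the requirement for a post-baseline assessment, because having one depends on what happens after treatment starts. Timing makes this real: "The first radiographic scan after receiving SUPLEXA will be performed at Week 6-12 weeks after the 1st SUPLEXA infusion". A subject who dies before that scan, or leaves without one, cannot be a RECIST responder. Removing that subject shrinks the denominator and leaves the numerator alone.

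The undefined population is a second gap. The main analyses of the other response-related endpoints have no denominator that an analyst could program. CBR is pulled two ways: to the Efficacy Evaluable Population by one sentence, and to the ORR approach, hence the Response Evaluable Population, by another.

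**Working it through.** **Which endpoint is meant.** Sections 1.1 and 3 list DLTs, AEs and SAEs as primary and ORR as secondary, and Section 9.3.2 itself introduces ORR as secondary. A set conditioned on RECIST scans has no role in analysing DLTs or AEs. The CBR sentence quoted above attaches the word primary to ORR. Within Section 9.3.2 the phrase therefore means ORR, and the label is a separate error.

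**Main against sensitivity.** Both use the Response Evaluable Population. No different assessor, confirmation rule or missing-data rule is given for the sensitivity analysis. For the same confirmation status, numerator, denominator and interval coincide, so the difference is exactly 0.

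**What separates this set from all treated subjects.** Inclusion criterion 3 already requires solid-tumour subjects to "Have 1 or more tumours measurable based on RECIST v1.1 as assessed by the local site Investigator". Apart from eligibility deviations, the post-baseline assessment is the only remaining filter.

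**Size.** The protocol gives no assumed ORR, no ORR-based sample size and no dropout rate, so there is no planned figure to reproduce. Let N be treated subjects with measurable disease, x responders and d the share with no post-baseline assessment.

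- All-treated ORR = x/N.
- Response Evaluable ORR = x/[N(1 - d)] = (x/N) × 1/(1 - d).

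The documents do not give d. For an assumed range the factor is:

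- d = 2%: 1/0.98 = 1.02
- d = 10%: 1/0.90 = 1.11
- d = 20%: 1/0.80 = 1.25
- d = 30%: 1/0.70 = 1.43

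Illustration with assumed N = 50 and x = 8. (Section 9.1 plans about 60 subjects over both cohorts and does not split them.) Intervals are Clopper-Pearson 95%.

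| Unscanned | d | Estimate | 95% CI | Shift (points) |
|---|---|---|---|---|
| 0 | 0% | 8/50 = 16.0% | 7.2-29.1 | 0 |
| 1 | 2% | 8/49 = 16.3% | 7.3-29.7 | 0.3 |
| 5 | 10% | 8/45 = 17.8% | 8.0-32.1 | 1.8 |
| 10 | 20% | 8/40 = 20.0% | 9.1-35.6 | 4.0 |
| 15 | 30% | 8/35 = 22.9% | 10.4-40.1 | 6.9 |

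The estimate would first pass the all-treated upper limit of 29.1% at 8/27 = 29.6%, which needs 23 of 50 unscanned (d = 46%), outside the assumed range.

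The shift depends on the response rate. With 2 responders, 2/50 = 4.0% becomes 2/35 = 5.7%, a shift of 1.7 points; with none, the estimate stays at 0. If ORR were also reported by tumour type, where Section 9.1 caps enrolment at about 8, an assumed 2/8 = 25.0% (3.2-65.1) would become 2/6 = 33.3% (4.3-77.7) with two unscanned.

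**The case against.** **Few subjects may go unscanned.** Sections 1.1 and 4.1.3 require the early termination visit in person, and the Schedule of Activities marks RECIST evaluation there. Section 7.2 continues tumour assessments after treatment stops for reasons other than progression. Section 5.2 excludes life expectancy under 6 months and ECOG 2 or worse. These limits are real and make 30% look high. They do not bring d to zero: Section 7.3 holds the termination visit only where possible, the schedule ties the evaluation to standard-of-care scan timing, and no visit recovers a subject who dies first.

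**The endpoints assigned to the Efficacy Evaluable Population may include ORR.** The wording allows it. ORR would then have two conflicting main populations, one of them undefined. The conditional analyses by central review change the assessor and name no other population. The text needs repair on either reading.

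**Bone-only disease.** Appendix 5 assesses it by modified MDA criteria, so such a subject could be scanned and still fall outside the set. This is marginal, because inclusion criterion 3 requires RECIST-measurable disease.

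**The SAP will settle it, and this is probably a drafting slip.** Both may be true. The current text still instructs the analyst otherwise. The only deadline is database lock, and the study is open-label, so the denominator could be settled after responses are known.

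**The priority is low.** ORR is secondary and descriptive, the study is non-comparative, and no documented decision rule rests on this estimate. That stands, and it limits how much weight the point carries. Listings (Section 9.3.1) should also let a reader identify unscanned subjects, although they do not change the reported ORR.

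**Conclusion.** The point holds. The sensitivity analysis written for ORR repeats the main analysis, and Section 9.3.2 relies on a population that Section 9.2 does not define. These are findings on the text; they rest only on reading the primary endpoint as ORR.

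The bias has one direction: any treated subject with measurable disease and no post-baseline assessment raises ORR, unless there are no responders. Its size cannot be known from the documents. Over the assumed d and the 8-in-50 illustration it is 0.3 to 6.9 points, smaller than the sampling error. No type I error or power is affected, and nothing in the documents ties this ORR to the possible expansion in Section 9.1. It should be corrected, but it does not threaten the primary safety objective.

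**What to change.** 1. In Section 9.2, define the Efficacy Evaluable Population as all subjects with at least one dose and measurable disease at baseline. The sponsor's intended definition is unknown; this one matches the main and sensitivity scheme already in Section 9.3.2.
2. In Section 9.3.2, run the main ORR and CBR analyses in that population, counting subjects with no post-baseline assessment as non-responders.
3. Keep the Response Evaluable Population for the sensitivity analysis, and report how many subjects it excludes and why.
4. Where Section 9.3.2 calls ORR primary, replace that word with secondary. In the sensitivity-analysis sentence, name ORR.
5. Carry the same definitions into the SAP.

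The cost is wording in Sections 9.2 and 9.3.2 and the SAP, with no new data collection. The reported ORR may be slightly lower.

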##### Secondary

- TTP will be defined as the time from the first dose of study intervention to the first documented date of disease progression.

##### Exploratory

- DOR will be defined as the time from the first date of objective response (CR or PR) to the first documented date of disease progression or the date of death due to any cause, whichever occurs first. Only subjects with a CR or PR will be included.
- TTR will be defined as the time from the first dose of study intervention to the first date of objective response (CR or PR). Only subjects with a CR or PR will be included.
- CBR will be defined as the proportion of subjects with a CR or PR or SD at 6 months.
- PFS will be defined as the time from the first dose of study intervention to the first documented date of disease progression or the date of death due to any cause, whichever occurs first.
- OS will be defined as the time from the first dose of study intervention to the date of death due to any cause.
- Biomarker change from baseline with time as % and absolute.

Main analyses of the above response-related endpoints will be performed in the Efficacy Evaluable Population using Investigator-assessed response. Sensitivity analyses of the above response-related endpoints may be performed in the Response Evaluable Population using Investigator-assessed response. If response is also assessed by BICR, further sensitivity analyses of the above response-related endpoints may be performed using BICR-assessed response.

CBR will be analysed in a similar manner as the primary endpoint of ORR.

Time-to-event endpoints (DOR, TTR, PFS, TTP, and OS) will be summarized using Kaplan-Meier estimates. If estimable, median, 25th, and 75th percentiles and associated 95% CIs will be presented. A Kaplan-Meier curve will also be generated for each time-to-event endpoint. For time-to event endpoints, censoring rules will be applied as follows. DOR will be censored at the last tumour assessment date. PFS and TTP will be censored at the last tumour assessment date

for subjects with post-baseline assessment (s). OS will be censored at the last known date alive for subjects.

### **Haematologic malignancies Cohort**

Statistical analyses will be descriptive and graphical in nature. If sample size permits, complete remission will be summarized descriptively using Kaplan-Meier medians and quartiles.

#### **9.3.3 Safety and Tolerability Analysis**

Safety outcomes will be analysed at the end of each study intervention period as well as over the course of the entire study.

The safety assessment will be based on the frequency of adverse events, on the observation of clinically significant abnormalities of laboratory values, concomitant medication use, vital signs, and physical examination data in the Safety analysis set.

Adverse events: Overall AE as well as AE classified by system organ class and preferred terminology according to the Medical Dictionary for Regulatory Activities (MedDRA) will be summarized. Additionally, AE will be summarized by severity and relation to study intervention. SAEs and AEs leading to discontinuation will also be summarized.

Other safety data: These data will be summarized by presenting the proportions of subjects with clinically significant abnormalities or changes from baseline values. Laboratory data will be presented in data listings and summarized.

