### 2.3.1 Risk Assessment

There are no identified or potential risks of particular severity anticipated based on toxicological data with SUPLEXA in animals, nor based on the mechanism of action and composition (an autologous population of NK and  $\gamma\delta$  T cells, CD8-positive and CD4-positive cells). Additionally, these cellular components have individually been evaluated in clinical studies and found to be well tolerated based on the lack of SAE (Section 2.2).

SUPLEXA is a first-in-class non-engineered autologous cell therapy. This study is ongoing and as of Sept 19 2022, more than 15 subjects were enroled in the study and received from 3 to 6 doses of SUPLEXA. No treatment-related SAE or adverse events had been reported.

Although nothing has been observed to date in blood chemistry, urinalysis, hematological or any labs, nor in any reported AE/SAE, potential risks based on the ongoing study and theoretical concerns that may be associated are presented below (Table 1) based on studies involving the autologous administration of CTL (Ohtani, 2014), CAR-T (Shivani, 2018) and dendritic cells

(Anguille, 2014) as well as the allogeneic administration of NK cells (Kyle B. Lupo, 2019), and  $\gamma\delta$  T cells (Pauza, 2018).

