##### **4.1.2.2 Subsequent Weekly Infusions (SUPLEXA Batch 1 and Batch 2)**

After completion of the first 3 weekly SUPLEXA batch 1 infusions, based on emerging data from prior subjects, disease evaluation (as described below), the discretion of the Investigator, and in agreement with the subject, treating physician and the Sponsor's Medical Monitor (or designee), the treatment period of SUPLEXA may be extended as follows:

Subjects will continue to receive SUPLEXA treatments of approximately 5 B cells, every 2 weeks with a wider window -1 day to +7 days until either, a) depletion of SUPLEXA batch 1 doses \*, or b) disease progression is assessed by the Investigator per iRECIST v1.1, or c) unacceptable toxicity, or other reasons for discontinuation as described in Section 7.2.

The 5 B cells will be provided as two bags of SUPLEXA targeted at 2.5B cells until all product used, unless there is only a single dose unit left, upon which time the subject may receive a single bag until more SUPLEXA is manufactured for them.

An additional SUPLEXA batch #2 may be manufactured for a subject based on (a) last dose of batch 1 and the investigator and subject and sponsor agree, then prior to the administration of the last SUPLEXA dose, blood can be drawn for SUPLEXA manufacturing of batch 2; or (b) > 2 weeks and < 8 weeks after the last dose of SUPLEXA administered, blood is collected for batch 2.

Note that subjects enroled in SUPLEXA-101, Version 3.0 or 2.0, and had SUPLEXA manufacturing started on or before October 31, 2022, may logistically be unable to have the consecutive administration of the recommended dosing regimen. These patients are therefore exempt from the defined gap in dosing, and the sequential dosing regimen described above. However, upon possible restarting additional doses of SUPLEXA, the dosing must be sequential until either, a) depletion of SUPLEXA batch 1 doses \*, or b) disease progression is assessed by the Investigator per iRECIST v1.1, or c) unacceptable toxicity, or other reasons for discontinuation as described in Section 7.2.

Subjects will be monitored at the clinic for at least 90 minutes (+/- 30 min) after each infusion for AE and ISR.

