#### **4.3 DOSE JUSTIFICATION FOR SUPLEXA THERAPEUTIC CELL DOSE**

The initial cumulative dose selected for this study was based entirely on preclinical mouse xenograft studies in which we dosed mice at ~28x the intended human regimen 3 clinical doses with an option to extend to 6 doses, with each dose approximately 2.5 B cells (range 1.9-3.9 B cells). Given the complete absence of treatment related adverse events for SUPLEXA in the ongoing human study, we propose that after the first 3 doses, administration of up to 14 additional treatments of 5B cells every 2 weeks will be well tolerated, and the actual number of doses depends on the SUPLEXA manufacturing yields for each of 2 patient-specific SUPLEXA batches.

The DSMB will provide an additional review of all safety data and predetermined points in the progress of the clinical study.

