## 9 STATISTICAL CONSIDERATION

### 9.1 SAMPLE SIZE DETERMINATION

Approximately 60 subjects will be enroled with a cap of about 8 subjects per individual tumour type (e.g., melanoma, breast, prostate, lung, haematological malignancies, etc.). If promising anti-tumour activity coupled with acceptable safety is observed, overall sample size and/or cap per tumour type may be expanded.

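### At least 16 of about 60 planned subjects were dosed while the plan was 3 to 6 doses of about 2.5B cells, and Section 9 has no summary by dose or regimen, so the planned tables cannot show safety at about 5B

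*Combined protocol and SAP*

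**What the plan says.** **Earlier exposure.** Section 2.3.1 reports that, as of 19 September 2022, "more than 15 subjects were enroled in the study and received from 3 to 6 doses of SUPLEXA", with no treatment-related events reported. Section 4.3 describes the initial plan as "3 clinical doses with an option to extend to 6 doses, with each dose approximately 2.5 B cells".

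**Current exposure.** The first three weekly infusions stay at about 2.5B. After that, Section 4.1.2.2 states: "Subjects will continue to receive SUPLEXA treatments of approximately 5 B cells, every 2 weeks". Section 4.3 proposes that "administration of up to 14 additional treatments of 5B cells every 2 weeks will be well tolerated". The extension is discretionary (Sections 4.1.2.2 and 4.4).

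**Transition.** Section 4.1.2.2 addresses subjects under Version 2.0 or 3.0 whose manufacturing started by 31 October 2022 and who may be unable, for logistical reasons, to follow the consecutive schedule: "These patients are therefore exempt from the defined gap in dosing, and the sequential dosing regimen described above". If such a subject restarts, dosing must be sequential. No count is given.

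**Analysis.** The sample size is given as "Approximately 60 subjects will be enroled with a cap of about 8 subjects per individual tumour type". The Safety Analysis Set in Section 9.2 is everyone given at least one dose. Section 9.3.3 summarises adverse events (AEs) overall, by system organ class and preferred term, by severity and by relationship. On timing it says "Safety outcomes will be analysed at the end of each study intervention period as well as over the course of the entire study". For the solid tumour cohort, Section 9.3.2 says "Other secondary and exploratory endpoints are defined as follows for the whole cohort or analysed by tumour type". No summary by dose, regimen or protocol version appears in Section 9.

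**The concern.** AE and serious adverse event (SAE) incidence is a primary endpoint (Section 3), and Section 4.2 says the study is meant to determine the recommended Phase 2 dose. That needs a view of safety at the dose given. The regimen changed during the study in both cells per infusion and possible cumulative exposure, yet the planned tables put all treated subjects into one denominator.

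Dose-limiting toxicity (DLT) data do not fill the gap. Section 6.5 places both DLT windows after the first and second infusions, which are 2.5B for everyone. The general AE tables are therefore the only planned summary evidence on 5B infusions, and they do not identify them. If toxicity is higher at 5B, an all-subject incidence would understate it.

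**Working it through.** **1. The plan's own figure.** The total of about 60 has no rate, precision or power behind it, so there is no calculation to reproduce. It is used here only as a denominator.

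**2. Share dosed before the change.** More than 15 means at least 16: 16/60 = 26.7%. The exact number is not given; if it were 20, the share would be 20/60 = 33.3%. Section 2.3.1 counts doses and not cells, so reading these as 2.5B doses relies on the plan described in Section 4.3.

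**3. Difference in exposure.**
- Earlier plan: 3 × 2.5B = 7.5B, up to 6 × 2.5B = 15B.
- Current proposal at its maximum: 7.5B + 14 × 5B = 77.5B.
- Ratio of maxima: 77.5/15 = about 5.2.

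**4. Does any planned split isolate 5B infusions?**
- *All treated subjects:* no. Both regimens are included.
- *Tumour type (efficacy):* no. It is unrelated to dose.
- *DLT windows:* no. They end before the third 2.5B infusion.
- *Study intervention period:* the term is undefined. In the Section 1.3 schedule, the first three infusions and the additional batch 1 doses sit under one Treatment Period heading, and the Treatment Extension Period is batch 2. Read that way, the first period mixes 2.5B and 5B even within a current subject. Cutting instead at dose 3 would separate the common phase, but the later part would still mix earlier doses 4 to 6 at 2.5B with current doses at 5B.

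**5. Possible effect of pooling (treatment-related AEs only).** Pooled rate = (m × p_earlier + (60 − m) × p_current)/60. The documents give no rates by regimen, so all rates are assumed. With m = 16 and p_current = 20% in the other 44:

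| p_earlier | Pooled rate |
|---|---|
| 0% | (0 + 8.8)/60 = 14.7% |
| 10% | (1.6 + 8.8)/60 = 17.3% |
| 20% | (3.2 + 8.8)/60 = 20.0% |
| 30% | (4.8 + 8.8)/60 = 22.7% |

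With m = 20 and p_earlier = 0%, the result is 8/60 = 13.3%. The first row takes the zero related events of Section 2.3.1 as lasting to study end. Zero in 16 still allows a true rate of up to 20.6% (exact two-sided 95% upper limit).

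**6. Precision after separation.** Exact 95% intervals: 9/44 = 20.5% (9.8% to 35.3%), against 9/60 = 15.0% (7.1% to 26.6%) if pooled with 0/16. With no events, the upper limit is 8.0% for n = 44 and 6.0% for n = 60. Not all 44 will reach 5B. If 50% to 75% did (assumed), 22 to 33 subjects would inform that dose.

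**The case against.** **Section 9 is only a summary.** Section 9.3 says a SAP finalised before database lock will give detailed methods and will supersede it. A regimen split could be specified there. This stands as a caveat, but the available text does not plan one.

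**Not everything is pooled.** It would go too far to say that every summary mixes the regimens: safety is also analysed by period, efficacy may be shown by tumour type, and individual data are listed (Section 9.3.1). This stands, but step 4 shows that no planned summary isolates 5B infusions, and listings are not summaries.

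**At least 16 subjects exempt?** A reader might infer this from Sections 2.3.1 and 4.1.2.2 together. The documents do not support it. The first counts subjects at 19 September 2022. The second depends on protocol version, manufacturing date and logistics, covers the dosing gap and sequence, and requires sequential dosing on restart. Section 4.1.2.2 also provides for extension in subjects already enrolled who have had three doses, so some earlier subjects may later receive 5B.

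**Is dilution established?** A reader might take it as fact. It needs a higher rate at 5B; it vanishes at equal rates and reverses if the earlier rate is higher. The reported zero covers treatment-related events only, not all AEs.

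**Does the same factor apply to objective response rate (ORR)?** No. ORR in Section 9.3.2 uses response-evaluable solid-tumour subjects, and the share of earlier subjects among them is not stated.

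**Comparing those who ever received 5B with the rest is biased.** This stands. Those subjects completed three doses and passed an extension decision that may rest on safety or clinical benefit, while time to progression (TTP) runs from first dose. It shapes the fix but does not excuse the gap.

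**Conclusion.** The point holds as a gap in the analysis plan. At least 16 of about 60 subjects (26.7%) were dosed while the plan was 3 to 6 doses of about 2.5B. The current text gives about 5B every 2 weeks after dose 3, and nothing planned in Section 9 summarises safety at that dose. This rests on the text alone and needs no assumption about event rates.

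The numerical effect is conditional. With 16 subjects at zero related events and 44 at 20%, pooling shows 14.7%, a relative loss of 26.7%, which is the most that 16 of 60 can cause. It would be smaller if earlier subjects also have events, if some later receive 5B, or if the study expands beyond 60. It would be larger if more than 16 subjects belong to the earlier group. The documents do not establish that rates differ by dose, how many subjects are exempt, or any figure for ORR. The change should be made before the table shells are fixed.

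**What to change.** Amend Sections 9.3.2 and 9.3.3, or specify in the SAP:

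1. Tabulate AEs and SAEs by the dose of the last infusion before onset (about 2.5B or about 5B), with the number of infusions and the number of subjects exposed at each dose as denominators. Use the dose actually given, because Section 4.1.2.2 allows a single bag when only one unit is left. The 2.5B infusions come first in each subject, so dose and time on study are confounded and the comparison is descriptive.
2. Present AEs/SAEs, ORR and TTP by the protocol regimen in force at first dose (earlier or current), plus total. This places every subject, including current subjects who stop after three 2.5B doses. For each group, report how many received any 5B infusion and how many fall under the exemption.
3. Label any efficacy summary of subjects who ever received 5B as descriptive, because they are selected for continuing past dose 3, and do not use it as the sole basis for conclusions.
4. Define study intervention period so that the first three infusions are separated from later ones.

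**Cost.** Smaller denominators and wider intervals in each column, as in step 6 of the working. The rest is text and table shells. Section 6.4 already requires a record of each dose given, but the minimum eCRF items it lists are dates, times and delays, so check that cells or bags per infusion reach the database.
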